6 SUPPORTING DOCUMENTATION

6.1 Non-key analysis specifications

6.1.1 Baseline characteristics and demographics

Unless otherwise specified, all summaries will be based on the RS.

6.1.1.1 Demographics

Demographic variables will be summarized using descriptive statistics by treatment group and overall on the RS for categories mentioned below.

Categories for continuous variables (including n, mean, SD, Median, Min and Max):

- Age at the time of first study entry (years),

Note: Missing age (captured on Demographics CRF) will be calculated as year of informed consent signed – year of birth

- Weight (kg),
- Height (cm),
- BMI (kg/m^2) calculated as: $BMI = \frac{\text{Weight (kg)}}{(\text{Height (m)})^2}$;

Categorical variables (using frequency counts and percentages):

- Age (18 -<65, 65 -<85, ≥ 85 years),
- Age (≤ 18 , 19 -<65, ≥ 65 years),
- BMI (<30 , $\geq 30 \text{ kg}/\text{m}^2$),
- Weight (35kg-<50 kg, 50-<70kg, 70-<100kg, ≥ 100 kg),
- Gender (Male, Female),
- Race (American Indian or Alaska native, Asian, Black, Native Hawaiian or Other Pacific Islander, White, Other/Mixed),
- Ethnicity (Hispanic or Latino, Not Hispanic or Latino),
- Region (North America, South America, Europe, Australia, Asia [excluding Japan], Japan and Africa),
- Country.

- Alcohol Use

A by-participant listing of demographics will be provided.

Childbearing potential will also be listed for the RS separately.

6.1.1.2 Baseline disease characteristics

The following variables will be summarized using descriptive statistics on the RS by treatment group and overall. All baseline characteristics will be provided in by-participant listings using the RS.

Continuous variables (including n, mean, SD, Median, Min and Max):

- Baseline RBANS score
- Baseline total IgG value
- Baseline LGI1 level

Categorical variables (using frequency counts and percentages):

- Baseline median category of seizure count over the Screening Period (1: 0 seizures, 2: 1-5 seizures, 3: 6-10 seizures, 4: 11-20 seizures, 5: >20 seizures)
- Time from disease onset (≤ 6 or > 6 months)
- Cognitive function (RBANS score of ≤ 85 or > 85)
- Baseline AIE medication
- Baseline mRS score

Notes:

- Historical seizures will be listed only:
 - Number of seizures (Week of any seizure experienced during the past 2 weeks prior to screening visit (week -2 or week -1))
 - Seizure description experienced during the past 2 weeks prior to screening visit
- Time from disease onset and cognitive function (RBANS score) will be based on the values recorded in the eCRF. This should be the same as the data entered into the interactive web response system (IWRS) at randomization, if for any reason eCRF values are missing then IWRS will be used.
- Baseline AIE medication will be collected in Prior and Concomitant Medication CRF where indication is AIE and presented by Preferred Terms.

6.1.2 Protocol deviations

A by-participant listing of important protocol deviations will be provided using the RS.

6.1.3 Medical history

Previous and ongoing medical history will be listed using the RS. Besides, procedure history will be provided in a separate by-participant listing using the RS.

6.1.4 Prior/concomitant/follow-up medications

Participants taking Past, Prior, Baseline, Concomitant or Concomitant Only medications will be listed using the RS by Anatomical Therapeutic Chemical (ATC) class, presenting as Anatomical Main Group (ATC Level 1), Pharmacological Subgroup (ATC level 3), PT, treatment group and overall. The number and percentage of participants taking rescue medications identified on CRF will be summarized using the RS.

Medications classified as past, prior, baseline, concomitant or concomitant only will be listed using the RS. A by-participant listing of concomitant procedures will also be listed using the RS. Originally reported dates will be used for listings.

6.1.4.1 Categories of prior and concomitant medications

Definitions:

- **Past Medications:** defined as any medications that started and stopped before the first administration of IMP.
- **Prior Medications:** defined as any medications that started before the first administration of IMP.
- **Baseline Medications:** defined as any medications that started prior to dosing and continued after (classified as prior and concomitant medications).
- **Concomitant Medications:** defined as any medications that have been taken at least once after the first administration of IMP during the Treatment and/or SFU Period.
- **Concomitant Only Medications:** defined as any medication that started after the first administration of IMP and continues during the Treatment and/or SFU Period.

Table 6-1 below summarizes concomitant medication classification with details around medication start and finish.

Table 6-1: Prior and Concomitant Medications Classification

Medication Started	Medication finished	Classification
Before 1st Dose IMP	Before 1st Dose IMP	Past
Before 1st Dose IMP	Any time	Prior
Before 1st Dose IMP	After 1st Dose IMP	Baseline (= prior and concomitant)
Any time	After 1st Dose IMP	Concomitant
After 1st Dose IMP	After 1st Dose IMP	Concomitant Only

6.1.4.2 Assignment of Treatment and/or SFU Period

The following rules will be used to assign a Prior, Baseline, Concomitant or Concomitant Only to following two study periods:

- **Treatment Period:** a medication will be assigned to the Treatment Period if the start date of the medication is on or after the date of the first administration of IMP on Day 1, up to 7 days following the final dose of IMP. This includes medications that started prior to the Treatment Period and those that continued into the SFU Period.
- **SFU Period:** a medication will be assigned to the SFU Period if it has been taken at least once from the day after Treatment Period to the EOS visit. This includes medications that started prior to the SFU Period.

6.1.5 Rescue medications

Rescue medication considered most appropriate for the study participant will be selected by the investigator. The study site will supply rescue medication that will be obtained locally. The effect of rozanolixizumab on the efficacy of IgG biologics and Fc-fusion proteins is not known.

6.1.6 Antiepileptic Drug (AED)

The number and percentage of subjects receiving AEDs (determined by medical review) over the course of the study will be summarized using the RS. Data will be presented at 6-week intervals (i.e., at Week 6, 12, 18 24 etc.).

6.1.7 Data derivation rules

6.1.7.1 Handling of dropouts or missing data

6.1.7.1.1 Efficacy data

Seizure freedom, time to seizure freedom, will be derived based on the weekly reported seizure frequency categories captured on Seizure Count CRF. Imputation methods to handle the missing data (including missing data due to intercurrent events)

In the case of all other endpoints (RBANS and mRS), the observed case method will be applied. This is also the case for any ordinal endpoints (EQ-5D-5L, CGI-S). No imputation of data will be applied.

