### **8.1.1 Assessment of seizures**

The primary objective of the study is to assess the efficacy of rozanolixizumab as measured by seizure freedom, where seizure freedom is defined by 28 consecutive days of no seizures, maintained until the end of the Treatment Period (Week 25). Seizures will be assessed during the treatment and SFU Period and the information will be recorded using a mobile device with a pre-installed application (app) which contains a seizure diary to be completed. The presence or absence of seizures will be recorded, and if seizures were present, the number of seizures and type of seizures will be recorded. Study participants or caregivers have up to 72 hours after the end of each day to complete the seizure diary in the mobile device app. The date of data entry will be captured in the audit trail. If seizure recording is not completed within the allotted time, it will no longer be available for completion and will show as blank in the data record. An overdue

or missed entry will not impact the availability of the next day's seizure diary, as each new calendar day triggers a new diary for completion. Retrospective edits to seizure diary entries recorded in the mobile device application are not allowed after 72 hours. Daily seizure documentation is submitted electronically to the investigator. A printout of electronic records will be reviewed and discussed with the patient to ensure completeness and accuracy during the next scheduled visit. If any changes are identified during this review, they must be documented on the paper printout. Data from the printout with updates as needed are entered into the eCRF. Printed records are filed as part of the participant's source documents at site.

As a result of the discussion, the investigator will assess the seizures according to the International League Against Epilepsy codes and record the seizure types and frequency on the printout of electronic records and eCRF; he/she will also confirm the presence of AEs (if applicable). Printed records will be filed as part of the participant's source documents at site.

The recording of seizures should begin from Visit 1 (Screening). At Visit 2 (Baseline), the printout of the electronic seizure diary from Screening must be reviewed for seizure data to confirm that the study participant meets eligibility criteria before randomization.

The study participant/caregiver should be educated on how to complete the electronic seizure diary daily.

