5.3 Primary Endpoint Analysis

5.3.1 Definition of endpoint

Participants who reported no seizures for 28 consecutive days and maintained the seizure count as zero until the end of Treatment Period will be treated as meeting the primary endpoint.

For the purpose of deriving the primary efficacy endpoint, any intermittent missing diary

seizure count recording will not be imputed but considered as non-zero for the purposes of the primary endpoint.

A by-participant listing of daily seizure count will be provided, including seizure freedom, time to first occurrence of seizure freedom, time to seizure freedom, and duration of seizure freedom.

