5.5 Exploratory Endpoints Analyses

5.5.1 Seizure control

Seizure frequencies will be recorded on a daily basis across the 24 weeks of randomized therapy and during a variable Screening Period, based on the following categories:

1. 0 seizures
2. 1-5 seizures
3. 6-10 seizures
4. 11-20 seizures
5. >20 seizures

For each participant, a median category of seizure count categories will be calculated for each week that the participant is in the randomized treatment period, such that each participant has one average median category for that week, along with a minimum and maximum category range. In case of missing seizure count category, calculated median category will be rounded up to fit into the 5 categories. For example, if the calculated median is 2.5, then this value will be rounded up to 3 as the final median.

For the Screening Period, a Baseline median category will be calculated for each participant, in the same way as described for each week of randomized treatment. This will be to utilize the screening data collected in the period up to 6 weeks immediately prior to randomization.

The frequency counts and percentages of participants falling into each of the median categories across the 24 weeks will be summarized by treatment group using RS.

In the case of 7 missing data points over an entire week, this will be imputed from the previous weeks data. For 1 week of data, the median will not be calculated if more than 5 missing values.

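### SAP 6.1.7.1.1 bases seizure freedom on weekly reported categories, which contradicts the daily definition of the primary endpoint in SAP 5.3.1

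*SAP*

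**What the plan says.** Under the data derivation rules, SAP 6.1.7.1.1 says: "Seizure freedom, time to seizure freedom, will be derived based on the weekly reported seizure frequency categories captured on Seizure Count CRF". The next sentence, on imputation methods for missing data, has no verb and breaks off.

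The rest of the plan works by day:

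- SAP 5.3.1 counts as meeting the primary endpoint "Participants who reported no seizures for 28 consecutive days and maintained the seizure count as zero until the end of Treatment Period". On gaps in the diary it says: "seizure count recording will not be imputed but considered as non-zero for the purposes of the primary endpoint".
- The same section promises: "A by-participant listing of daily seizure count will be provided, including seizure freedom, time to first occurrence of seizure freedom". Two further items in that listing are duration and time to seizure freedom.
- SAP Table 1-1 defines time to first occurrence of seizure freedom (TTFSF) as a number of days from randomization to the first day of the first 28-day run. SAP 5.5.2 measures duration from the first to the last seizure-free day and treats missing daily counts as non-zero.
- SAP 5.5.1: "Seizure frequencies will be recorded on a daily basis across the 24 weeks of randomized therapy". Protocol 8.1.1 says that a missed entry does not block the next one, "as each new calendar day triggers a new diary for completion".

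The only weekly seizure category that the SAP defines is the weekly median of the daily categories, used for seizure control (5.5.1) and for the Baseline category (5.1.1.1.6). SAP 6.7 declares no change from the protocol-planned analyses.

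**The concern.** The SAP gives two sources for the same endpoint, and they are not interchangeable. A record with one value per week cannot show the first day of a seizure-free run, cannot confirm 28 consecutive days unless the run lines up with the week boundaries, and cannot apply a rule that acts on single missing days. Two programmers, one following 5.3.1 and the other 6.1.7.1.1, could classify the same participant differently.

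That classification enters the odds ratio and 95% CI in SAP 5.3.2, the onset and duration outputs, and the PK and IgG listings by primary-endpoint status (5.7.1.1.1 and 5.7.1.2.1).

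**Working it through.** The plan gives no figure on this point. The powers in SAP Table 3-1 are for 60 participants and do not depend on it. The check below asks what a weekly rule would do if it were applied.

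**Inputs.** The endpoint is a run of at least 28 seizure-free days that reaches the end of treatment (SAP 5.3.1). The end of treatment is the actual EOT visit date (SAP, end date of the Treatment Period). That visit falls 1 week after the final dose (Protocol 4.4), and doses are 7 ± 2 days apart (Protocol Table 1-1, footnote l), so it need not fall on a week boundary. Nominal Week 25 starts on Day 24 × 7 + 1 = 169.

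**Assumptions, not stated in the documents.** Weeks are 7-day bins from first dose (Days 1–7, 8–14 and so on), the weekly record is zero only if all 7 days are clear, and a weekly success needs four complete zero weeks at the end.

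**1. False failures.** If treatment ends on Day E, the last complete week ends on Day E − (E mod 7). Four complete weeks therefore need a run of 28 + (E mod 7) days. True responders with shorter runs are lost.

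| E | E mod 7 | Run needed (days) | True responders scored as failures |
|---|---|---|---|
| 166 | 5 | 33 | runs of 28–32 days |
| 167 | 6 | 34 | runs of 28–33 days |
| 168 | 0 | 28 | none |
| 169 | 1 | 29 | runs of exactly 28 days |
| 170 | 2 | 30 | runs of 28–29 days |
| 171 | 3 | 31 | runs of 28–30 days |
| 172 | 4 | 32 | runs of 28–31 days |

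Example at Day 169: the last seizure is on Day 141 and Days 142–169 are clear, which is 28 days. The daily rule gives a success. Week 21 (Days 141–147) is non-zero, so only Weeks 22, 23 and 24 are complete zero weeks, and the weekly rule gives a failure.

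If a partial last week were counted as a week, the error would reverse. At Day 169 the last four bins start on Day 148, so a run of 169 − 148 + 1 = 22 days would pass.

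**2. Onset.** The first complete zero week starts 0 to 6 days after the true first seizure-free day. If start days are spread evenly over the week, the mean delay is (0+1+2+3+4+5+6)/7 = 3 days.

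**3. If the weekly category were the 5.5.1 median.** The median of 7 daily categories is the 4th ordered value. It stays at the zero category when up to 3 days have seizures, so four such weeks can hold 4 × 3 = 12 seizure days. Section 5.5.1 also allows a median with up to 5 missing days, that is from 2 recorded days, whereas 5.3.1 counts each intermittent missing day as non-zero.

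**4. Weight of one participant.** SAP Section 3 gives 12 participants. The split by arm is not given. With 6 in an arm, one reclassification moves the rate by 1/6 = 17 points; with 5 or 7 it is 20 or 14 points. Illustration with 6 per arm: 4/6 versus 2/6 gives OR = (4×4)/(2×2) = 4, and one active-arm responder fewer gives (3×4)/(2×3) = 2. If the only placebo responder were lost, the OR would not be estimable and SAP 5.3.2 would switch to another estimator.

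**The case against.** The strongest reply is that the daily rule already governs. It stands in the section that defines the endpoint, with a missing-day rule and a daily listing in which a reader could see any misclassification. The weekly sentence sits under non-key specifications, next to an unfinished sentence, and looks like leftover text.

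It may not even describe weekly aggregates. Under Protocol 8.1.1 the daily entries are reviewed at the next scheduled visit and then entered in the eCRF. With doses about a week apart, weekly reported could mean daily categories transcribed each week. The documents do not show the layout of the Seizure Count CRF.

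The sentence also names time to seizure freedom, whereas the secondary endpoint is TTFSF. SAP 5.3.1 lists the two as separate items, so the sentence does not clearly reach the secondary endpoint.

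All of this stands as a limit on the point. A reader might infer that the primary endpoint will be derived from weekly data and that the daily information is lost. The documents do not support that: daily data are collected, and a daily rule is written down. The reply does not remove the contradiction. The weekly sentence is phrased as a derivation rule, nothing says that 5.3.1 prevails, and the broken sentence after it supplies no bridge.

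**Conclusion.** The SAP contains an unresolved contradiction about the source of its primary endpoint. Severity is moderate. Under the stated assumptions on weekly aggregates, false failure is confined to runs of 28 to 33 days and depends on the actual EOT date, and onset would be resolved only to the week. The output affected is a descriptive odds ratio with its CI, the onset and duration outputs, and listings by primary-endpoint status in 12 participants. SAP Section 2 and 5.3.2 rule out hypothesis testing.

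Two stronger readings are tempting and not supported:

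- A 28-day run placed anywhere on the calendar covers four complete weeks for only 1 of 7 start days, and only a run of 34 days or more always does. A reader might infer that six in seven true 28-day responders would be failed. The primary-endpoint run must reach the end of treatment, so the loss follows the EOT date, as in the table.
- A reader might infer that someone with seizures on 3 days of every week would pass. That needs the weekly category to be the 5.5.1 median, which the documents do not establish. Section 5.5.1 describes that median as calculated, for an exploratory endpoint, while 6.1.7.1.1 speaks of categories that are reported and captured on a CRF.

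**What to change.** Replace the sentence in SAP 6.1.7.1.1 with:

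> Seizure freedom, time to first occurrence of seizure freedom, time to seizure freedom and duration of the seizure-free period will be derived from the daily seizure records, with intermittent missing days counted as non-zero (Section 5.3.1).

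Use weekly median categories only for the seizure-control and Baseline-category summaries. Complete or delete the unfinished imputation sentence. Naming 5.3.1 matters because Table 5-1 in SAP 5.1.3 gives a different treatment of missing daily counts for the primary endpoint and should be aligned at the same time.

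With daily records as the source, week-boundary misclassification disappears and onset is exact to the day. The cost is a short SAP edit and the matching programming specification; no new data are needed. Before finalizing, confirm that the Seizure Count CRF holds daily entries. If it does not, name the dataset that does.

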#### **7.1.3 Permanent discontinuation due to absence or loss of clinical benefit**

Study participants **must be permanently discontinued from IMP** if they do not experience a clinical improvement within the first 4 weeks of the Treatment Period (ie, an absence of clinical benefit) or if they experience clinical worsening (ie, a loss of clinical benefit) at any time as defined by any of the following:

1. mRS assessment
  - a. Worsening of 1 point compared with Baseline; or
  - b. Lack of improvement of a severe score (4 or 5) after 4 weeks
2. Worsening of cognitive function: A decrease of  $\geq 8$  points in the total RBANS score compared to Baseline, and per the assessment of the investigator that the study participant has worsened
3. A clinically meaningful recurrence of seizures of a previously experienced type or a new seizure type, either of those requiring a change in therapy (per the assessment of the investigator)
4. Lack of seizure improvement (per the assessment of the investigator)

If study participant permanently discontinues from IMP for any reason, investigators should contact the medical monitor, whenever possible, to discuss the withdrawal of a participant in advance. Study participants who permanently discontinue the IMP should complete the assessments outlined for the EOT/EDisc Visit and enter the 8-week SFU Period. If IMP is permanently discontinued, the requirement for, and selection of, rescue therapy will be made by the investigator.

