### 9.3.2.1 Change in cognitive function: RBANS

**Table 9-2: Estimands for the secondary efficacy endpoint: RBANS**

Statistical category	Estimand:		
	Treatment: Randomized rozanolixizumab or placebo in study participants who are concurrently treated with iv or oral steroids.	Population: Study participants with LGI1 AIE as specified in the inclusion and exclusion criteria (Section 5.1 and Section 5.2), respectively.	Endpoint (Variable): Change from Baseline in RBANS total scale index score at the end of the Treatment Period (Week 25).
Intercurrent events: The study participant: 

1. Temporarily discontinued from the IMP

2. Permanently discontinued from the IMP

	Analysis set	Intercurrent event handling strategy	Population-level summary (Analysis):
Secondary	RS	1. Treatment policy strategy: Temporary discontinuation of the IMP will not affect the assessment of the endpoint.	The mean change from Baseline in RBANS total scale index score at Week 25 will be estimated using the MMRM approach utilizing information across all the available scheduled visit outcomes for

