5.1.1.1.4 Mapping of assessments performed at Early Discontinuation Visit

Assessments performed at EDisc Visit will be assigned to the next scheduled site visit (following the last scheduled visit that the participant completed prior to EDisc Visit) where each assessment is evaluated as per protocol. This approach means that there is a chance that EDisc Visit will be mapped to different visits according to the schedule of assessments.

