5.4.1 Change in cognitive function (RBANS)

RBANS 5 domain index scores and total scale index score will be captured and calculated at the Screening visit, then post-Baseline visits 8, 16, 26, early treatment discontinuation visit and end of study visit according to the RBANS US v2.0 (13Nov2019) (see [Section 6.2](#)). The last available results of RBANS scores prior to first dose will be served as Baseline.

The observed Baseline and post-Baseline RBANS total scale index score at each scheduled visit where RBANS is collected will be summarized using descriptive statistics by randomized treatment group, together with the changes from Baseline. A by-participant listing of RBANS scores will be provided.

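### The Week 25 observed-case RBANS mean omits participants withdrawn before completing Visit 26, including those stopped for RBANS decline, so an affected arm is likely to look too favourable

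*SAP*

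**What the plan says.** Protocol 7.1.3 lists "Worsening of cognitive function" among the reasons for mandatory permanent discontinuation. It is defined as a fall of at least 8 "points in the total RBANS score compared to Baseline, and per the assessment of the investigator that the study participant has worsened". Both parts are required. The same section adds: "Study participants who permanently discontinue the IMP should complete the assessments outlined for the EOT/EDisc Visit and enter the 8-week SFU Period". RBANS is part of the EOT/EDisc assessments in the protocol's Schedule of Activities.

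SAP 5.4.1 places RBANS at Screening, "then post-Baseline visits 8, 16, 26, early treatment discontinuation visit and end of study visit". That sentence does not name the Week 25 visit, although the endpoint is change at Week 25.

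SAP 5.1.1.1.4 says: "Assessments performed at EDisc Visit will be assigned to the next scheduled site visit", meaning the next one at which that assessment is due. It notes that "there is a chance that EDisc Visit will be mapped to different visits according to the schedule of assessments".

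SAP 6.1.7.1.1 says: "In the case of all other endpoints (RBANS and mRS), the observed case method will be applied", without imputation. SAP 5.4 and 5.4.1 plan only descriptive statistics by arm and visit, plus a listing.

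The protocol had planned something else. In Table 9-2, "The mean change from Baseline in RBANS total scale index score at Week 25 will be estimated using the MMRM approach", using all scheduled visits, with a hypothetical strategy for permanent discontinuation. SAP 6.8.1 explains that the analyses were cut back because only 12 participants were randomized.

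**The concern.** RBANS at Week 25 is the first secondary endpoint. A confirmed fall on RBANS is itself a reason to stop study drug, and for most of the Treatment Period a stop means no Week 25 value. The Week 25 mean is then selected on the outcome it describes.

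Under the planned MMRM, a low score assigned to Visit 16 or Visit 26 would still have informed the Week 25 estimate. In an observed-case mean it does not. Dropping the model with 12 participants is reasonable, but no Week 25 summary that uses these scores was put in its place. A reader of the Week 25 row could credit an arm with cognitive gain that partly reflects who is left in it. The other stopping reasons in protocol 7.1.3 (mRS worsening, seizure recurrence, lack of seizure improvement) can add further outcome-related loss.

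**Working it through.** The plan gives no effect size, SD of change or withdrawal rate for RBANS, so there is no planned figure to reproduce.

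**Step 1: where an EDisc score lands.** Visits 8, 16 and 26 fall at Weeks 5, 13 and 21; EOT is Week 25. Under SAP 5.1.1.1.4:

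| Last scheduled visit completed before EDisc | EDisc RBANS counted at | In the Week 25 row? |
|---|---|---|
| Visit 8 or later, before Visit 16 | Visit 16 | No |
| Visit 16 or later, before Visit 26 | Visit 26 | No |
| Visit 26 or later | Week 25 | Yes |

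A stop before Visit 8 is completed is likewise counted at Visit 8 and is absent at Week 25.

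**Step 2: effect on one arm.** Let n be the arm size, k the number omitted, S the mean change in those who stay and D the mean EDisc change in those omitted. The observed-case mean is S. With the EDisc scores counted, the mean is [(n - k)S + kD]/n = S - (k/n)(S - D). The observed-case mean is therefore higher by (k/n)(S - D) whenever S exceeds D.

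**Step 3: effect on the difference.** Assumed for illustration: n = 6 per arm (12 participants, if balanced), S = +6 on rozanolixizumab and +3 on placebo, D = -8. Each omission raises the rozanolixizumab mean by 14/6 = 2.33 and the placebo mean by 11/6 = 1.83. The observed-case difference is always 6 - 3 = 3.0.

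| Omitted, rozanolixizumab / placebo | Difference with EDisc scores counted | Leaving them out |
|---|---|---|
| 0 / 1 | 6.00 - 1.17 = 4.83 | shrinks it |
| 0 / 2 | 6.00 - (-0.67) = 6.67 | shrinks it |
| 1 / 2 | 3.67 - (-0.67) = 4.33 (before rounding) | shrinks it |
| 1 / 1 | 3.67 - 1.17 = 2.50 | widens it |
| 1 / 0 | 3.67 - 3.00 = 0.67 | widens it |
| 2 / 1 | 1.33 - 1.17 = 0.17 (before rounding) | widens it |

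It is unchanged when (k/n)(S - D) is the same in both arms.

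**Step 4: simulation with the stopping and mapping rules applied.** Assumptions:
- SD of change 15 x sqrt(2 x (1 - 0.7)) = 11.6, using the protocol's normative SD of 15 and an assumed Baseline correlation of 0.7.
- Correlation between changes at different visits 0.5.
- True mean change rising linearly to 8 (rozanolixizumab) and 2 (placebo) at Week 25.
- Every fall of 8 or more at Visits 8, 16 or 26 confirmed by the investigator.

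Of those randomized, 28% (20.5% + 7.7%) on rozanolixizumab and 35% (23.4% + 11.4%) on placebo are stopped at Visit 8 or 16 and are absent at Week 25. The arm means rise from 8.0 to 10.2 and from 2.0 to 4.4. The difference moves from 6.0 to 5.8. With the SD on rozanolixizumab 1.4 times larger, the rozanolixizumab mean rises from 8.0 to 12.0 and the difference widens from 6.0 to 7.6. With equal true means and SDs, the difference stays at 0.

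The upward shift of the arm means is consistent across these runs. The direction for the difference is not.

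**The case against.** A reader might infer that the Week 25 mean contains only participants who have not declined. The documents do not support that. A stop after Visit 26 is counted at Week 25, a fall first seen at the Week 25 visit removes nobody, and a fall that the investigator does not judge to be worsening leaves the participant in. A reader might also infer that the treatment difference is biased toward zero, and size the loss by cutting off the Week 25 distribution at -8. That models a different rule, and Steps 3 and 4 show that the direction is open.

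The strongest defence is that little depends on this row. The SAP plans no RBANS difference, interval or test, and states that the sample is too small for the efficacy objectives. With 6 per arm and an SD of change of 8 to 15, the standard error of a difference is SD x sqrt(2/6), or 4.6 to 8.7 points. SAP 5.4.1 lists every score by participant, SAP 5.2 tabulates discontinuation reasons by arm, and the mapped EDisc score appears in the table at its earlier visit.

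It can also be said that the added row resembles last observation carried forward and departs from the protocol's hypothetical strategy. That is fair. In the two simulation settings with a true difference of 6.0, using the EDisc score for everyone stopped gave differences of 5.5 and 2.9, further from 6.0 than the observed-case row. The added row is no better an estimate of that target; it shows what the Week 25 row leaves out.

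These points limit the consequence. They do not change the fact that the printed Week 25 mean is selected on outcome, and the listing leaves the reader to work that out.

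**Conclusion.** The point holds for arm means. Anyone withdrawn before completing Visit 26 is absent from the Week 25 RBANS summary, and for those stopped under the RBANS criterion the absence is tied to the outcome. The Week 25 mean of an arm with such withdrawals is likely to look too favourable, by (k/n)(S - D) relative to a mean that counts their EDisc scores. With six per arm and the assumed values, that is about 2 points per omitted participant.

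The documents do not fix the number of such withdrawals, their depth or their split by arm. The size is therefore unknown, and the difference between arms may shrink, hold or widen. If no arm has such a withdrawal, this mechanism has no effect. With 12 participants and descriptive reporting the consequence is modest, but the correction is cheap enough to make.

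**What to change.** In SAP 5.4.1, keep the by-visit observed-case table and show n at each visit. Name the Week 25 visit in the list of RBANS visits, which now gives the end of study visit instead. Then:

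- Add one descriptive row by arm: change from Baseline at the end of the Treatment Period, taken at Week 25 or, for those who stopped earlier, from the EDisc score. Show n, because anyone without an EDisc RBANS will still be missing.
- Beside it, show the number per arm discontinued for cognitive worsening. If the discontinuation reason on the case report form is not that specific, derive the count from the listings.
- State that Week 25 is interpreted from the two rows together.

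This follows the plan's own conventions. The SAP ends the Treatment Period at the EDisc visit for those who discontinue, and protocol Table 9-3 uses the discontinuation assessment in place of Week 25 for mRS.

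The cost is a table row, a count and a sentence or two, from data already collected. The drawback is that the row mixes assessment times from early in treatment to Week 25, so it should not replace the Week 25 row.
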